### Expansion cohort (additional 10 patients accrued) will be treated as follows:

Ibrutinib 420 mg po once daily with

Rituximab 375 mg/m^2 IV weekly x4

If, based on above toxicity criteria, the Ibrutinib 420 mg daily dose schedule has been discontinued, then 280 mg po once daily will be the expansion cohort dose schedule

If, based on above toxicity criteria, the Ibrutinib 280 mg daily dose schedule has been discontinued, then 140 mg po once daily will be the expansion cohort dose schedule

### Duration of therapy:

Ibrutinib -> 420 mg daily (or adjusted dose) will continue until progression of cGVHD or development of significant side effects.

Rituximab -> there is the potential for a 2nd weekly x4 Rituximab course 8 weeks after initial therapy, if no response or an incomplete response is noted.

If, based on above toxicity criteria, the Ibrutinib 280 mg daily dose schedule has been discontinued, then 140 mg po once daily will be the expansion cohort dose schedule

### Duration of therapy:

Ibrutinib -> 420 mg daily (or adjusted dose) will continue until progression of cGVHD or development of significant side effects.

Rituximab -> there is the potential for a 2nd weekly x4 Rituximab course 8 weeks after initial therapy, if no response or an incomplete response is noted.

## **9 Data Handling and Record Keeping**

### **9.1 Confidentiality**

Information about study subjects will be kept confidential and managed according to the requirements of the Health Insurance Portability and Accountability Act of 1996 (HIPAA). Those regulations require a signed subject authorization informing the subject of the following:

- What protected health information (PHI) will be collected from subjects in this study
- Who will have access to that information and why
- Who will use or disclose that information
- The rights of a research subject to revoke their authorization for use of their PHI.

In the event that a subject revokes authorization to collect or use PHI, the investigator, by regulation, retains the ability to use all information collected prior to the revocation of subject authorization. For subjects that have revoked authorization to collect or use PHI, attempts should be made to obtain permission to collect at least vital status (i.e. that the subject is alive) at the end of their scheduled study period.

### **9.2 Source Documents**

Source data is all information, original records of clinical findings, observations, or other activities in a clinical trial necessary for the reconstruction and evaluation of the trial. Source data are contained in source documents. Examples of these original documents, and data records include: hospital records, clinical and office charts, laboratory notes, memoranda, subjects' diaries or evaluation checklists, pharmacy dispensing records, recorded data from automated instruments, copies or transcriptions certified after verification as being accurate and complete, microfiches, photographic negatives, microfilm or magnetic media, x-rays, subject files, and records kept at the pharmacy, at the laboratories, and at medico-technical departments involved in the clinical trial.

### **9.3 Case Report Forms**

The study case report form (CRF) is the primary data collection instrument for the study. All data requested on the CRF must be recorded. All missing data must be explained. If a space on the CRF is left blank because the procedure was not done or the question was not asked, write "N/D". If the item is not applicable to the individual case, write "N/A". All entries should be printed legibly in black ink. If any entry error has been made, to correct such an error, draw a single straight line through the incorrect entry and enter the correct data above it. All such changes must be initialed and dated. DO NOT ERASE OR WHITE OUT ERRORS. For clarification of illegible or uncertain entries, print the clarification above the item, then initial and date it.

### **9.4 Records Retention**

It is the investigator's responsibility to retain study essential documents for at least 2 years after the last approval of a marketing application in their country and until there are no pending or contemplated marketing applications in their country or at least 2 years have elapsed since the formal discontinuation of clinical development of the investigational product.

## **10 Study Monitoring, Auditing, and Inspecting**

### **10.1 Medical Monitoring**

It is the responsibility of the Principal Investigator to oversee the safety of the study at his/her site. This safety monitoring will include careful assessment and appropriate reporting of adverse events as noted above, as well as the construction and implementation of a site data and safety-monitoring plan (see Section 10.2). Medical monitoring will include a regular assessment of the number and type of serious adverse events.

## **10.2 Safety and Data Monitoring**

This study will be monitored by the Data Safety Monitoring and Accrual Committee (DSMAC) of the Norris Cotton Cancer Center. The Committee meets quarterly to review accrual rates and information for studies that have accrued participants. The Clinical Cancer Review Committee (CCRC) determines the frequency of DSMAC review. The DSMAC has the authority to suspend or to recommend termination to the CCRC of all research activities that fall within its jurisdiction. In the event that a study is suspended or terminated, that information will be forwarded to the CPHS (Dartmouth IRB) office.

## **10.3 On-Site Monitoring**

Clinical research monitoring for regulatory compliance and data integrity will be conducted according to the NCI-approved NCCC Data and Safety Monitoring Plan. Internal monitoring is conducted by appropriately trained staff of the NCCC Office of Clinical Research and Dartmouth-Hitchcock Medical Center Clinical Trials Office who are not involved in the study. This monitoring will include periodic assessment of the regulatory compliance, data quality, and study integrity. Study records will be reviewed and directly compared to source documents, and the conduct of the study will be discussed with the investigator. Monitors may request access to all regulatory documents, source documents, CRFs, and other study documentation for on-site inspection. Direct access to these documents is guaranteed by the investigator, who must provide support at all times for these activities.

## **10.4 Auditing and Inspecting**

The investigator will permit study-related monitoring, audits, and inspections by the EC/IRB, government regulatory bodies, and Dartmouth compliance and quality assurance groups of all study related documents (e.g. source documents, regulatory documents, data collection instruments, study data etc.). The investigator will ensure the capability for inspections of applicable study-related facilities (e.g. pharmacy, diagnostic laboratory, etc.). Participation as an investigator in this study implies acceptance of potential inspection by government regulatory authorities and applicable Dartmouth compliance and quality assurance offices.

# **11 Ethical Considerations**

This study is to be conducted according to US and international standards of Good Clinical Practice (FDA Title 21 part 312 and International Conference on Harmonization guidelines), applicable government regulations and Institutional research policies and procedures.

This protocol and any amendments will be submitted to a properly constituted independent Ethics Committee (EC) or Institutional Review Board (IRB), in agreement with local legal prescriptions, for formal approval of the study conduct. The decision of the EC/IRB concerning the conduct of the study will be made in writing to the investigator and a copy of this decision will be provided to the sponsor before commencement of this study. The investigator should provide a list of EC/IRB members and their affiliate to the sponsor.

All subjects for this study will be provided a consent form describing this study and providing sufficient information for subjects to make an informed decision about their participation in this study. This consent form will be submitted with the protocol for review and approval by the EC/IRB for the study. The formal consent of a subject, using the EC/IRB- approved consent form, must be obtained before that subject undergoes any study procedure. The consent form must be signed by the subject or legally acceptable surrogate and the investigator-designated research professional obtaining the consent.

# **12 Study Finances**

## **12.1 Funding Source**

This research protocol is not currently sponsored, though funding is being requested in the form of a 2018 NCCC Pilot (PROUTY) Grant.

## **14 Attachments**

**Attachment 1:** Chronic GVHD Assessment (26)

**Attachment 2:** Response Determination Table for Chronic GVHD Clinical Trials (27)

# CHRONIC GVHD ASSESSMENT

Patient: \_\_\_\_\_ Date of Visit: \_\_\_\_\_

MRN: \_\_\_\_\_ Completed by: \_\_\_\_\_

Form adapted from Jagasia, MH, BBMT 21 (2015) 389-401.

Karnofsky Performance Score		SCORE 0	SCORE 1	SCORE 2	SCORE 3	

		 Asymptomatic and fully active (KPS 100%)	 Symptomatic, fully ambulatory, restricted only in physically strenuous activity (KPS 80-90%)	 Symptomatic, ambulatory, capable of self-care, >50% of waking hours out of bed (KPS 60-70%)	 Symptomatic, limited self-care, >50% of waking hours in bed (KPS <60%)	
Skin†		None	SCORE 0	SCORE 1	SCORE 2	SCORE 3
Score by % BSA Check all that apply:  Maculopapular rash/Erythema  Lichen-planus features  Sclerotic features  Papulosquamous lesions or ichthyosis  Keratosis pilaris-like GVHD			 No BSA Involved	 1-18% BSA	 19-50% BSA	 >50% BSA
Cutaneous features score†			 No Sclerotic Features		 Superficial sclerotic features, "not hidebound"	Check all that apply  Deep sclerotic features  "Hidebound", impaired mobility  Ulceration
Other skin features not scored by BSA Check all that apply:  Hyperpigmentation  Hypopigmentation  Poikiloderma  Severe or generalized pruritus  Hair or nail involvement			† Skin scoring should use both percentage of BSA involved by disease signs and cutaneous features score. When a discrepancy exists between the percentage of total body surface area score and the skin features score, OR if superficial sclerotic features are present (score 2), but there is impaired mobility or ulceration (score 3), the higher level should be used for final skin scoring.			
 Abnormality present, but explained entirely by documented non-GVHD cause (specify): _____						
Mouth		None	SCORE 0	SCORE 1	SCORE 2	SCORE 3
Lichen planus-like features present?  Yes  No			 No Symptoms	 Mild symptoms with disease signs but not limiting oral intake significantly	 Moderate symptoms with disease signs with partial limitation of oral intake	 Severe symptoms with disease signs on examination with major limitation of oral intake
 Abnormality present, but explained entirely by documented non-GVHD cause (specify): _____						
Eyes		None	SCORE 0	SCORE 1	SCORE 2	SCORE 3
Keratoconjunctivitis sicca (KCS) confirmed by Ophthalmologist?  Yes  No  Not examined			 No Symptoms	 Mild dry eye not affecting ADL; requiring lubricant drops ≤3 x per day	 Moderate dry eye sxs partially affecting ADL (requiring lubricant eye drops >3 x per day or punctal plugs), WITHOUT new vision impairment due to KCS	 Severe dry eye symptoms significantly affecting ADL (eyeware to relieve pain) OR unable to work because of ocular sxs OR loss of vision due to KCS
 Abnormality present, but explained entirely by documented non-GVHD cause (specify): _____						
Liver		None	SCORE 0	SCORE 1	SCORE 2	SCORE 3

			 Normal total bilirubin and ALT or AP < 3 x ULN	 Normal total bilirubin with ALT ≥3 to 5 x ULN or AP ≥ 3 x ULN	 Elevated total bilirubin but ≤3 mg/dL or ALT > 5 x ULN	 Elevated total bilirubin > 3 mg/dL
 Abnormality present, but explained entirely by documented non-GVHD cause (specify): _____						
Lungs		None	SCORE 0	SCORE 1	SCORE 2	SCORE 3
Symptom score*			 No Symptoms	 Mild symptoms (SOB after one flight of steps)	 Moderate symptoms (SOB after walking on flat ground)	 Severe symptoms (SOB at rest; requiring oxygen)
FEV1 score*  PFT not Done			 FEV1 ≥80%	 FEV1 60-79%	 FEV1 40-59%	 FEV1 ≤39%
* Lung scoring should be performed using both the symptom and FEV1 scores when possible. FEV1 should be used in the final lung scoring where there is a discrepancy between symptoms and FEV1 scores.						
 Abnormality present, but explained entirely by documented non-GVHD cause (specify): _____						

# CHRONIC GVHD ASSESSMENT

Patient: \_\_\_\_\_ Date of Visit: \_\_\_\_\_

MRN: \_\_\_\_\_ Completed by: \_\_\_\_\_

*Form adapted from Jagasia, MH, BBMT 21 (2015) 389-401.*

GI Tract	None	SCORE 0	SCORE 1	SCORE 2	SCORE 3

Check all that apply:
  Esophageal web/proximal stricture or ring  Dysphagia  Anorexia  Nausea  Vomiting  Diarrhea  Weight loss $\geq$ 5% within 3 months  Failure to thrive		 No Symptoms	 Symptoms without significant weight loss (<5%)	 Symptoms associated with mild to moderate weight loss within 3 months (5-15%) OR moderate diarrhea without significant interference with daily living	 Symptoms associated with >15% weight loss within 3 months, requires nutritional supplement for most calorie needs OR esophageal dilation OR severe diarrhea with significant interference with daily living

Abnormality present, but explained entirely by documented non-GVHD cause (specify): \_\_\_\_\_

Genital Tract s	None	SCORE 0	SCORE 1	SCORE 2	SCORE 3

 Not examined Currently sexually active
  Yes  No		 No signs	 Mild signs † and females with or without discomfort on exam	 Moderate signs † and may have symptoms with discomfort on exam	 Severe signs † with or without symptoms

s To be completed by a specialist or trained medical providers.

Abnormality present, but explained entirely by documented non-GVHD cause (specify): \_\_\_\_\_

## JOINTS AND FACIA NEXT PAGE

### Other GVHD Manifestations

 Other indicators, clinical features or complications related to chronic GVHD (check all that apply and assign a score to severity (0-3) based on functional impact where applicable none – 0, mild -1, moderate -2, severe – 3)		
 Ascites (serositis) _____	 Myasthenia Gravis _____	 Eosinophilia > 500/ $\mu$ l _____
 Pericardial Effusion _____	 Peripheral Neuropathy _____	 Platelets <100,000/ $\mu$ l _____
 Pleural Effusion(s) _____	 Polymyositis _____	
 Nephrotic syndrome _____	 Weight loss >5% without GI symptoms _____	

### Global Severity Score – Please check one.

Mild	1 or 2 organs involved with no more than score 1 PLUS lung score 0
Moderate	3 or more organs involved with no more than score 1 OR At least 1 organ with a score of 2 (not lung) OR Lung score 1
Severe	At least one organ with a score of 3 OR Lung score 2 or 3

- In Skin: higher of the 2 scores is used for global severity.
- In Lung: FEV1 is used instead of clinical score for global severity.
- If the entire abnormality in an organ is noted to be unequivocally explain by a non-GVHD cause, that organ is not included in the global severity score.
- If the abnormality in an organ is attributed to multifactorial causes (GVHD plus other causes), the scored organ will be used for calculation of the global severity score, regardless of the contributing causes. (No downgrading of the organ severity score.)

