### 3.3 Secondary Study Endpoints

1. Response rate of clinically significant GVHD based on NIH criteria (from 2014 NIH Consensus Development Project, see Attachment 1) at the following time points: six weeks, three months, and six months after initiation of therapy.
2. Laboratory correlates: The following serum biomarkers will be checked at the specified time points: pre-treatment; six weeks; three months; six months.

Elisa/Luminex	Flow Cytometry
sIL2Ra	CD146
CX3CLI	CCR5
CXCL9	
CXCL10	
CCL22	
CCL4	
ST2	FOXP3

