## 4 Subject Selection and Withdrawal

### 4.1 Inclusion Criteria

Patients fulfilling the following criteria will be eligible for registration onto this study:

1. Men and women  $\geq 18$  years old who are recipients of an allogeneic bone marrow, cord blood or peripheral blood stem cell transplant.  
(There will be no restrictions based upon underlying disease, donor source, degree of HLA match, intensity of pre-transplant conditioning regimen or use of prior donor lymphocyte infusion(s).)
2. Chronic GVHD that is confirmed by clinical assessment and/or biopsy.
3. Either steroid-refractory or steroid-dependent cGVHD.
4. Karnofsky performance status  $\geq 60$ .

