#### **See Attachments:**

**Attachment 1:** Chronic GVHD Scoring Assessment – Clinician (26)

**Attachment 2:** Response Determination Table for Chronic GVHD Clinical Trials (27)

The timeframe for assessments will be as follows: baseline (pre-treatment); 6 weeks, 3 months and 6 months after initiation of therapy.

The mode of assessment will include the following (to be undertaken by a limited number of team members who will do these assessments, so as to ensure consistency and minimize subjectivity).

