## 7 Statistical Plan

## 7.1 Statistical Methods

GVHD response rates based on the GVHD Global Severity Score and Clinical Assessment ( Attachment 1) at 6 weeks, 3 months and 6 months will be assessed using exact binomial methods combining the initial dose escalation and expansion cohorts. With the expansion cohort after the safety dose escalation phase, a total of 15 patients will be available for evaluation. An exact test for proportions with a null hypothesis of a 15% response rate, an alternative hypothesis of a 50% response rate, and a one-sided significance level of 0.10, would have a power of 85% using 15 subjects, including a Bonferroni correction for looking at the 6 week, 3 month and 6 month response rates. This test rejects the null hypothesis if 6 out of 15 subjects respond. If only the 10 subjects from the expansion cohort are used, the null is rejected if 4 out of 10 respond, and the power is reduced to 0.83. Calculations were done in the PASS 2008 package.

Two-sample t-tests for continuous data and Fisher's exact test for binary data will be used to compare responders and non-responders for the purpose of identifying independent *biomarker* correlates of treatment response. The power and precision of these comparisons will depend on the number of responders and non-responders compared.

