### CLINICIAN ASSESSMENT - Since the last evaluation, this patient's cGVHD is:

# CHRONIC GVHD ASSESSMENT

[figure not shown]
Patient: \_\_\_\_\_ Date of Visit: \_\_\_\_\_

MRN: \_\_\_\_\_ Completed by: \_\_\_\_\_

*Form adapted from Jagasia, MH, BBMT 21 (2015) 389-401.*

+3 Very much better	+2 Moderately better	+1 A little better	0 About the same	-1 A little worse	-2 Moderately worse	-3 Very much worse
Since the last evaluation, have immunosuppression and/or steroid therapy dosages been changed?						
Comments:						

JOINTS AND FASCIA	None	SCORE 0	SCORE 1	SCORE 2	SCORE 3
 P-ROM score (see below)  Shoulder (1-7): _____ Elbow (1-7): _____ Wrist/finger (1-7): _____ Ankle (1-4): _____		 No symptoms	 Mild tightness of arms or legs, normal or mild decreased range of motion (ROM) AND not affecting ADL	 Tightness of arms or legs OR joint contractures, erythema thought due to fasciitis, moderate decrease ROM AND mild to moderate limitation of ADL	 Contractures WITH significant decrease of ROM AND significant limitation of ADL (unable to tie shoes, button shirts, dress self, etc.)
 Abnormality present but explained entirely by non-GVHD documented cause (specify): _____					

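### Section 7.1 tests response on a severity score that has no category for resolved disease and no room for Mild entrants to improve, instead of the Attachment 2 response table that Section 5.1.2 adopts

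*Combined protocol and SAP*

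**What the plan says.** **The test.** Section 7.1 analyses "GVHD response rates based on the GVHD Global Severity Score and Clinical Assessment", both taken from Attachment 1, at 6 weeks, 3 months and 6 months. It sets a 15% null rate against a 50% alternative, at one-sided 0.10 with a Bonferroni correction for the three time points. The null is rejected with 6 responders of 15, and the stated power is 85%. The section does not say what change makes a subject a responder.

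**The first item.** Attachment 1 is headed "Global Severity Score – Please check one". The choices are Mild, Moderate and Severe. Mild is "1 or 2 organs involved with no more than score 1" together with a lung score of 0.

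**The second item.** The form carries a seven-point change scale from +3 to -3, introduced by "CLINICIAN ASSESSMENT - Since the last evaluation, this patient's cGVHD is". I take this to be what 7.1 calls the Clinical Assessment.

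**Entry.** Section 4.1 asks for "Chronic GVHD that is confirmed by clinical assessment and/or biopsy" and "Either steroid-refractory or steroid-dependent cGVHD". Section 4.3 adds that the disease must be active. Neither sets a minimum NIH severity.

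**Response elsewhere in the protocol.** Section 3.3 names the endpoint as "Response rate of clinically significant GVHD based on NIH criteria" and points to Attachment 1. Section 5.1.2 adopts Attachment 2 as the response determination table. Section 6 schedules the formal assessments on the Attachment 1 forms, but judges improvement as at least a partial response by NIH response criteria.

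**The concern.** A severity score is being used to measure response, and its scale stops short at the good end. A subject whose cGVHD has cleared must be ticked Mild, which is false, or left blank, which may be handled as missing. A subject who starts at Mild has no lower box.

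The change scale does not clearly repair this, because it compares each visit with the last evaluation. It also has no stated responder threshold, and no rule links it to the severity score. Two analysts could follow 7.1 faithfully and count different numbers of responders among 15 subjects.

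Response is a secondary endpoint; the primary one is safety. But this response rate carries the only powered hypothesis test in the protocol. The same responder classification also splits subjects for the biomarker comparisons in 7.1, so a misclassified subject affects both analyses.

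**Working it through.** **1. Reproduce the stated design.** Inputs from 7.1: n = 15, null 0.15, alternative 0.50, one-sided 0.10, three time points. The level per look is 0.10/3 = 0.0333.

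- Reject at 6 or more: P(X ≥ 6 | 15, 0.15) = 0.0168, within 0.0333.
- Reject at 5 or more: P(X ≥ 5 | 15, 0.15) = 0.0617, above 0.0333. So 6 is the right cut-off.
- Power: P(X ≥ 6 | 15, 0.50) = 1 − 4944/32768 = 0.849, which matches the stated 85%.

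**2. Follow two hypothetical subjects through the instruments.**

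| Subject | Global Severity Score | Change scale | Attachment 2 |
|---|---|---|---|
| Moderate at baseline; every organ clear at 6 weeks and still clear at 3 and 6 months | No valid box at any of the three visits | Better at 6 weeks; could be rated unchanged at 3 and 6 months, because the comparison is with the last evaluation | Organ-level complete response can be recorded |
| Mild at baseline with skin and eyes at score 1; skin clears, eyes unchanged | Mild, then Mild | Can be rated better | Complete response in skin; no overall rule across organs is written |

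**3. Size of the Mild ceiling, under stated assumptions.** Suppose that response means a fall of at least one Global Severity category and nothing else, that m of the 15 subjects enter as Mild, that the others respond at 50%, and that the cut-off stays at 6. Mild entrants then contribute no responders, so power = P(X ≥ 6 | 15 − m, 0.50). For m = 2 this is 1 − (1 + 13 + 78 + 286 + 715 + 1287)/8192 = 1 − 2380/8192 = 0.709.

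| Mild entrants m | Able to respond | Overall expected rate, 0.5(15 − m)/15 | Power |
|---|---|---|---|
| 0 | 15 | 50.0% | 0.849 |
| 1 | 14 | 46.7% | 0.788 |
| 2 | 13 | 43.3% | 0.709 |
| 3 | 12 | 40.0% | 0.613 |
| 4 | 11 | 36.7% | 0.500 |

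The documents give no value for m.

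**4. Dependence on the missing combination rule.** If both items must improve, the Mild ceiling binds in full. If improvement on either is enough, a Mild entrant can respond and the ceiling does not apply. If Attachment 2 is the rule, it does not apply either. Section 7.1 does not say which holds.

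**5. Can Attachment 2 be completed from the Attachment 1 form?** Not entirely, on the form text that could be read (one figure is not shown):

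- Mouth: the table uses the modified OMRS; the form has a 0 to 3 symptom score.
- Gut: the table has separate esophagus, upper GI and lower GI scores; the form has one GI score.
- Global: the table uses a 0 to 10 clinician overall severity score; the form has the three-category tick box.

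**The case against.** The strongest reply is that the protocol has more than one way to register improvement. Section 7.1 names two items, and a Mild entrant can be rated better on the change scale. Every organ row on the form allows a score of 0, so full resolution can be worked out even if the global box is blank. Attachment 2 defines complete response by organ and globally, and Section 5.1.2 adopts it. All of this stands, and it rules out several stronger inferences.

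- A reader might infer that the trial cannot record a complete response. It can, through organ scores of 0 and Attachment 2. The gap is in the Global Severity Score only.
- A reader might infer that Mild entrants are certain non-responders. That needs a responder rule based on the Global Severity Score alone, or one requiring improvement on both items. The documents state neither.
- A reader might infer that the 85% power is not reached. The plan applies its 50% to all 15 subjects, and at that overall rate the power is 0.849. The lower figures come from giving the 50% to non-Mild subjects only, which lowers the overall rate.
- A reader might infer that Mild entry is common, or that the subjects enrolled do not have clinically significant GVHD. No expected case mix is given. Active steroid-refractory or steroid-dependent disease may leave few Mild subjects, and the term in Section 3.3 is not defined.

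The reply does not settle which measure the test in 7.1 uses. That section does not cite Attachment 2, its second item is not anchored to baseline, and the form it names lacks some inputs that Attachment 2 requires.

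**Conclusion.** The point holds in a limited form. Section 7.1 rests its powered test on severity-form items and gives no responder rule, while Sections 5.1.2 and 6 rely on response criteria. One of those items cannot classify a subject with no remaining disease and cannot show improvement from Mild, a baseline state that the entry criteria allow.

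The power loss is conditional. It runs from 0.849 down to 0.788, 0.709, 0.613 and 0.500 for 1 to 4 Mild entrants, provided that the Global Severity Score alone decides response and the remaining subjects respond at 50%. It is zero with no Mild entrants or with Attachment 2 as the rule. The missing category and the unstated responder rule do not depend on these assumptions.

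This should be corrected before analysis. It concerns a secondary endpoint and does not touch the primary safety objective.

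**What to change.** In 7.1, define a responder at each time point as a subject with complete or partial response versus baseline by the Attachment 2 criteria. Write out one overall rule that turns the organ and global rows into a single result. This brings 7.1 into line with Sections 5.1.2 and 6.

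Make sure that the assessment form collects what the table needs: the modified OMRS, separate esophagus, upper GI and lower GI scores, and the 0 to 10 clinician overall severity score.

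If the Global Severity Score is kept as a supporting measure, add a box for None (no organ involved), count reaching None as a response from any baseline category, and tabulate response by baseline category. The extra box alone would not be enough: it would leave the responder rule undefined and 7.1 at odds with Sections 5.1.2 and 6, and a Mild entrant with partial improvement still could not respond on that score.

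The cost is slightly more form-filling at the existing baseline, 6-week, 3-month and 6-month assessments, and a revised sentence in 7.1. No extra subjects or visits are needed.
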